7.3 Final Analysis Plan

An objective of this study is to determine PK parameters (C_{max}, AUC and ratio of stratum corneum drug concentration during uptake and clearance) of lidocaine in healthy adults and DPK data after using Lidoderm[®] (lidocaine 5% patches) and Mylan 5% lidocaine patches for the purpose of IVIVC by collecting data over two separate periods. Complimentary *in vitro* data will be collected using human skin.

Secondly the objective is to investigate the influence of heat application on the PK parameters of lidocaine after using a RLD and generic patches along with no heat application. The primary PK parameters to be compared are 1) C_{max}, before and after heat application and 2) AUC before and after heat application consistent with similar PK studies¹³⁻²³. Analysis of variance (ANOVA) followed by post-hoc Bonferroni test will be used for comparing the differences in the means of the PK parameters and significant differences will be declared at p<0.05. The statistical comparisons will be conducted as follow:

If lidocaine PK concentrations are found to be non-normally distributed, then we will examine Box-Cox transformations (e.g., log, square-root, etc.) that can achieve normality. If no transformation can achieve normality, then will use permutation tests to compute empirical *p*-values, and will use the bootstrap to compute standard errors and confidence intervals that account for within-person correlation.

IVIVC will be conducted comparing PK parameters and profiles to predicted PK parameters and profiles using IVPT and *in vitro* DPK results. Multiple methods will be implemented to develop an IVIVC. The first method is to compare the steady state concentrations. The predicted steady state concentration using our current IVPT data will employ the following formula:

$$C_{ss} = \frac{J_{ss} * A}{CL}$$

The second method will compare the PK profiles of the clinical and IVPT study by predicting lidocaine concentrations at each time point in the IVPT study and comparing it to the clinical PK profile. The third method will be to determine and compare residual patch analysis between *in vitro* and *in vivo*.

In terms of developing an IVIVC for the DPK study a comparison will be made between *in vitro* and *in vivo* uptake and clearance lidocaine amounts. The second method is to compare the clearance to uptake lidocaine amount ratio between *in vitro* and *in vivo*.

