B) Dermatopharmacokinetics (DPK) of Lidocaine Patches

- Lidocaine products (6 sites/product, 3 sites/arm/product) will be applied to each arm. All of the patchpieces will be removed at 10 h. Four patch sites will be tape stripped (uptake or absorption) at 10 h, four patch sites (two sites/product/time point) will be tape stripped (clearance) at 15 and 24 h.

- Tape strips applied and removed after patch piece removal to determine the drug concentration in stratum corneum, which is the outer barrier layer of the epidermis.

C) Residual Drug Analysis of Lidocaine Patches

In conjunction with the above described study, residual drug analysis will also be conducted for the used patches described in Part A.

- Prior to administration to the Subject as described in Part A, patches will be weighed and the weight recorded.
- The pouch, release liner and all items coming into contact with the patches (gloves, forceps, etc..) applied in Part A will be retained for analysis.
- The used patches will be retained for drug content analysis.
- All items coming into contact with the patches during removal from the Subject will be stored in a separate labeled Ziploc bag until analyzed for drug content.

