7 PHARMACOKINETICS AND STATISTICAL CONSIDERATIONS

7.1 Study Hypothesis

DPK and PK

We will test the null hypothesis (H_0) that the mean clearance/uptake lidocaine amount ratio, and the PK parameters (C_{max} and AUC) between the lidocaine patch products are different (i.e., outside the 80–125% range).

Heat

Due to differences in inactive ingredients between RLD and generic lidocaine patches, the release rate of lidocaine may differ from these patches upon exposure to heat. As a result, in this study the influence of standardized heat application (two heat periods) on the pharmacokinetics (PK) parameters of lidocaine will be studied after using Lidoderm[®] (reference) and Mylan lidocaine (generic) patches. Analysis will be to determine whether heat differentially impacts lidocaine serum concentrations between Lidoderm[®] (reference) and Mylan (lidocaine) patches. We will test the null hypothesis (H_0) that the coefficient for the patch-by-heat interaction equals zero, adjusting for time.

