7.2 Analyses

Lidocaine concentrations will be measured in serum samples collected from each subject. Blood samples (approximately 3 mL (0.6 tsp)) will be collected during the Study Sessions 1, 2, 3, 4, 5 and 6. During Study Session 1 and 2 within 60 min before dosing and then at 2 hours, 3 hours, 3 hours 55 minutes, 4 hours 50 minutes, 5 hours 30 minutes, 6 hours, 6 hours 30 minutes, 7 hours, 8 hours 25 minutes, 9 hours 20 minutes, 10 hours, 10 hours 30 minutes, 11 hours, 11 hours 30 minutes, 12 hours, 13 hours, 14 hours and 15 hours post-patch application. Blood samples (approximately 3 mL (0.6 tsp)) will be collected during Study Sessions 3 and 5 within 60 min before dosing and then at 2 hours, 3 hours, 3 hours 55 minutes, 4 hours 5 minutes, 4 hours 20 minutes, 4 hours 35 minutes, 4 hours 50 minutes, 5 hours 5 minutes, 5 hours 30 minutes, 6 hours, 6 hours 30 minutes, 7 hours, 8 hours 25 minutes, 9 hours 20 minutes, 10 hours, 10 hours 30 minutes, 11 hours, 11 hours 30 minutes, 12 hours, 13 hours, 14 hours and 15 hours post-patch application. Blood samples (approximately 3 mL (0.6 tsp)) will be collected during Study Sessions 4 and 6 within 60 min before dosing and then at 2 hours, 3 hours, 3 hours 55 minutes, 4 hours 50 minutes, 5 hours 30 minutes, 6 hours, 6 hours 30 minutes, 7 hours, 8 hours 25 minutes, 8 hours 35 minutes, 8 hours 50 minutes, 9 hours 5 minutes, 9 hours 20 minutes, 9 hours 35 minutes, 10 hours, 10 hours 30

minutes, 11 hours, 11 hours 30 minutes, 12 hours, 13 hours, 14 hours and 15 hours post-patch application. DPK will be conducted at 10 h (skin drug uptake) or 5 h and 14 h (skin drug clearance) post patch application. Non compartmental analyses (NCA) will be conducted to estimate the PK parameters such as: maximum serum concentration (C_{max}); apparent elimination rate constant (k); apparent half-life (t_{1/2}), calculated as 0.693/k; AUC_{0-last} of the serum concentration–time determined by the linear trapezoidal method; and AUC value extrapolated to infinity (AUC_{inf}), calculated as the sum of AUC_{0-last} and the area extrapolated to infinity: AUC_{inf} = AUC_{0-last} + C_{last}/k where C_{last} would be the last quantifiable concentration. All NCA analyses will be conducted using Phoenix[®] WinNonlin[®] 6.4 (Pharsight, a Certara Company, CA).

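### Section 7.1 sets an 80–125% null for the two products, but the only test of means visible in section 7.3 is a difference test, which cannot reject it

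*Combined protocol and SAP*

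**What the plan says.** All places are in the combined protocol and SAP.

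- **Section 7.1, DPK and PK.** The null for the mean clearance/uptake ratio, Cmax and AUC is that these measures "between the lidocaine patch products are different (i.e., outside the 80–125% range"). Rejecting it means concluding equivalence. The limits appear nowhere else in the visible text.
- **Section 7.1, Heat.** A separate null of the difference type: the patch-by-heat interaction coefficient is zero, adjusting for time.
- **Section 7.3.** The paragraph that opens "Secondly the objective is to investigate the influence of heat application on the PK parameters of lidocaine" contains the test: "Analysis of variance (ANOVA) followed by post-hoc Bonferroni test will be used for comparing the differences in the means of the PK parameters". The decision rule attached to this test reads: "significant differences will be declared at p<0.05". The paragraph ends with the lead-in "The statistical comparisons will be conducted as follow", after which the visible text turns to non-normality.
- **Section 7.3, fallback.** "If no transformation can achieve normality, then will use permutation tests to compute empirical" p-values, with bootstrap standard errors and confidence intervals. No confidence level and no equivalence limits are given.
- **Section 7.2.** Two AUCs are defined, one to the last quantifiable concentration, "determined by the linear trapezoidal method; and AUC value extrapolated to infinity".
- **Protocol Summary, part B.** After uptake sampling at 10 h, "four patch sites (two sites/product/time point) will be tape stripped (clearance) at 15 and 24 h".

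**The concern.** A null of non-equivalence is rejected by showing that the product ratio lies inside the limits. A difference test asks whether the ratio departs from 1. A significant result does not say whether the ratio is inside or outside 80–125%, and a non-significant one says nothing about the limits. An analyst who follows the visible text therefore cannot decide the first hypothesis that section 7.1 lists.

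The limits and the three measures are fixed in advance. What is left open is which AUC is meant, which clearance time enters the ratio, how the two sites per product and time point are combined, and which interval has to fall inside the limits. Those choices could be made after the data are seen. Section 2.2 places the research in the context of approval pathways for generic topical products, so a statement about 80–125% from this study should rest on a rule written beforehand.

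**Working it through.** **1. Place the two nulls side by side.** Let R be the Mylan/Lidoderm ratio for one measure.

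| | Null | What rejection shows |
|---|---|---|
| Section 7.1, products | R ≤ 0.80 or R ≥ 1.25 | 0.80 < R < 1.25 |
| Section 7.3, ANOVA/Bonferroni | R = 1 (equal means) | R differs from 1 |

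Neither outcome in the second row answers the first. This step needs no figure for variability.

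**2. Look for another route in the visible text.** ANOVA is a named model and 0.05 a named level, and an ANOVA error term could supply an interval for R. The plan does not say that it will, and nothing compares an interval with the limits. The bootstrap intervals arise only if no transformation achieves normality, and they carry no limits either. If the ANOVA sentence is meant for heat alone, as its position suggests, the product null is left with no visible test.

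**3. Count the versions of each measure.** AUC: two (AUC0-last and AUCinf). Clearance/uptake ratio: two (clearance at 15 h and at 24 h, over uptake at 10 h). Cmax: one.

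**4. Illustrate that the two decisions can disagree.** The documents give no power calculation and no CV, so there is no stated figure to reproduce. From the documents: 12 subjects, each their own control, limits 0.80 and 1.25. Assumed: log scale, paired analysis with 11 df, within-subject CV as shown, observed ratio 0.90.

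SE = √(2·ln(1+CV²)/12); t = ln(0.90)/SE, with ln(0.90) = −0.1054; 90% CI = exp(ln(0.90) ± 1.796·SE).

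| CV | SE | t | Two-sided p | 90% CI | Difference test, unadjusted | 80–125% |
|---|---|---|---|---|---|---|
| 5% | 0.0204 | −5.16 | 0.0003 | 0.868–0.934 | significant | inside |
| 25% | 0.1005 | −1.05 | 0.317 | 0.751–1.078 | not significant | not shown |

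The plan does not state the Bonferroni family. If all pairs of the six PK sessions are compared, there are 6×5/2 = 15, and the CV 5% result becomes 15 × 0.00031 = 0.005, still significant. The CV 25% result is not significant with or without adjustment. The disagreement in both directions therefore survives that adjustment.

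**5. Power of an equivalence rule at 12 subjects.** Two one-sided tests at 5%, which amount to requiring the 90% CI to lie within 0.80–1.25, true ratio 1, same SE formula, integrated over the error variance:

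| Assumed CV | Power, one measure |
|---|---|
| 20% | 0.653 |
| 25% | 0.355 |
| 30% | 0.161 |

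The chance that several measures all pass can be no higher than the power for any one of them.

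**The case against.** The strongest objection is that the rule may exist. Section 7.3 announces a set of comparisons and the visible text then moves to another subject, so a list or table may have been lost in reading the PDF, at the place where a product rule would stand. Text lost in that way is not missing from the plan. This stands, and it makes the point conditional.

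Second, sections 3.1 and 3.2 make no equivalence claim. The stated purpose is PK and DPK data for an IVIVC, and section 2.2 already calls the Mylan patch an approved generic. This also stands and limits the weight of the point. It does not remove it, because section 7.1 says the hypothesis will be tested.

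Third, an illustration must allow for the Bonferroni step. At CV 10% the same observed ratio gives an unadjusted p of 0.0253, which becomes 0.0505 with only two comparisons. Whether a ratio inside the limits is also significant thus depends on the CV and on the family. That is accepted: the example shows that disagreement is possible, not how often it would occur.

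A reader might go further and infer that the sponsor will take a non-significant result as proof of equivalence. The plan states no such rule, so no false-equivalence rate can be attributed to it.

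**Conclusion.** The point holds for the visible text. The 7.1 product null cannot be rejected by the test of means shown in section 7.3, and no visible text links an interval to the 80–125% limits. This rests on logic alone. The figures for p, CI and power rest on an assumed CV and a paired log-scale analysis, and only illustrate the size.

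The reach is narrow: the product comparison in section 7.1. A reader might infer that the study's main aims are compromised; they are not, because the PK profiles and the IVIVC comparisons do not use this test. A reader might also infer that no equivalence rule exists at all; the possible loss of text after the lead-in in section 7.3 rules out that certainty. If the lost text holds such a rule, the point falls. If not, this is a clarification to make before the product comparison is analysed, and not a fault that stops the study. Confidence is moderate for that reason.

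**What to change.** First confirm whether a list follows the lead-in in section 7.3. If it holds no equivalence rule, do one of the following.

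**Option A: supply the rule in section 7.3.**
- PK: compare Session 2 with Session 1 (no heat) on Cmax and one named AUC.
- DPK: name the clearance time for the clearance/uptake ratio (15 h, 24 h or both) and say how the two sites per product and time point are combined.
- For each measure, use a within-subject log-scale analysis and report the Mylan/Lidoderm geometric mean ratio with its 90% CI.
- Reject the 7.1 null for a measure only if the whole CI lies within 80.00–125.00%. Make an overall equivalence statement only if every measure passes.
- State that ANOVA/Bonferroni does not test the product null. Also reconcile it with the heat null of section 7.1, which is a patch-by-heat interaction adjusting for time; post-hoc comparison of means is not visibly that test.

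**Option B: withdraw the 80–125% hypothesis** and report the ratios with their CIs. This is clean only if the product comparison data have not been examined. If they have, disclose when the change was made.

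**Cost.** Wording in sections 7.1 and 7.3, and no new data. The price of option A is power: at 12 subjects and a true ratio of 1, about 65%, 35% and 16% for one measure at assumed CVs of 20%, 25% and 30%, and no higher for all measures jointly. An overall equivalence statement could well fail even for identical products. The plan should say so, and this makes option B a serious alternative.
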